4.1. Inclusion Criteria

Subjects meeting all the following criteria will be eligible to be enrolled in the study:

9. Patient is able to understand the meaning of the study and is willing to sign the EC approved, study specific Informed Patient Consent Form.
10. Patients with a pre-operative knee score of < 70.
11. Patients scheduled to undergo primary total knee replacement with any of the following indication.
 - Painful and disabled knee joint resulting from osteoarthritis.
 - One or more compartments are involved.
12. Need to obtain pain relief and improve function.
13. Ability and willingness to follow instructions, including control of weight and activity level, and to return for follow-up evaluations.
14. A good nutritional state of the patient.
15. Full skeletal maturity of the patient, patients who are at least 18 years of age.
16. Patients of either sex.

4.2. Exclusion Criteria

Subjects meeting any of the following criteria will not be included in the study:

1. The subject is morbidly obese, defined as Body Mass Index (BMI) of > 40.
2. Skeletal immaturity of the patient, patients who are less than 18 years of age.
3. Patient has a flexion contracture of 15° and more.
4. Patient has a varus/valgus contracture of 15° and more.

5. Patients with a pre-operative knee score of >70.
6. The subject has a history of total or unicompartmental reconstruction of the affected joint.
7. The subject will be operated bilaterally.
8. Patients who had a Total Hip Arthroplasty (THA) on contralateral and/or ipsilateral side within the last year that is considered to have an unsatisfactory outcome (Patients with contralateral and/or ipsilateral THA > 1 year ago with good outcome can be included in the study).
9. Patients who had a Total Knee Arthroplasty (TKA) on contralateral side within the last 6 months that is considered to have an unsatisfactory outcome. (Patients with contralateral TKA > 6 months ago with good outcome can be included in the study).
10. The subject has an active or suspected latent infection in or about the knee joint
11. Osteomyelitis
12. Sepsis.
13. Patients who will need lower limb joint replacement for another joint within one year.
14. The subject has a neuromuscular or neurosensory deficiency, which would limit the ability to assess the performance of the device.
15. The subject has a systemic or metabolic disorder leading to progressive bone deterioration.
16. The subject is immunologically suppressed or receiving steroids in excess of normal physiological requirements.
17. The subject's bone stock is compromised by disease or infection which cannot provide adequate support and/or fixation to the prosthesis.
18. The subject has had a knee fusion to the affected joint.
19. Female patients planning a pregnancy during the course of the study.
20. The patient is unable or unwilling to sign the Informed Consent specific to this study

4.3. Discontinuation and Withdrawal of Subjects

The subject's participation in this investigation is voluntary, and the subject has the right to refuse further participation or withdraw from this investigation at any time and without providing a reason.

4.3.1 Specific Criteria for Withdrawal /Termination

In the event that a subject is discontinued from the study for any reason, the site will complete a Study Termination form. Subjects may be withdrawn for the following reasons:

- Patient failure – defined by the requirements at the two- year follow-up interval see section 6.1.3.
- Any Serious Adverse Event that effects the outcome of the study
- Any Serious Adverse Event related to the test device
- Revision/Removal of study device
- Patient withdrawal (patients own request)
- Lost to Follow-Up

- If, in the Investigator's opinion, continuation in the study would be detrimental to the subject's well being (a written explanation is required)
- Completion of study and final evaluation
- Death of the subject

If the patient fails to return for their follow-up appointments, every effort should be made to contact the subject to assess their health status. If after attempting to contact the patient through 3 documented phone calls and a certified (i.e., return-receipt) letter, the patient still does not respond, the patient will be considered as "lost to follow-up". A Study Termination Form will be completed after notifying Stryker of the patient's status.

In the event that the subject is discontinued by the investigative site prior to the final study evaluation, the subject is notified that they are no longer in the study and a Study Termination form will be completed.

Following discontinuation, the subject will be seen regularly as considered clinically appropriate. If the discontinuation was caused by an adverse event the subject will be seen regularly until the symptoms have disappeared or are under control, or until feasible treatment has been undertaken. Refusal to participate or early withdrawal from this investigation will not affect the quality or availability of the subject's medical care.

Subjects withdrawn from the study will keep their subject number. New subjects must always be assigned a new subject number. In the event that the subject withdraws from this investigation, the information that has already been collected will be included in the database and in the final analyses. The subject's medical records will also be available for monitoring, auditing and inspection purposes.

After withdrawal subjects will not be replaced to the study.

5. Subject Enrolment

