11.1.	INTERNATIONAL STANDARDS	32
11.2.	DELEGATION OF INVESTIGATOR DUTIES	32
11.3.	SUBJECT INFORMATION AND INFORMED CONSENT	32
11.4.	PATIENT INSURANCE	32
11.5.	PERSONAL DATA PROTECTION/CONFIDENTIALITY	32
11.6.	LEGAL APPROVALS, ANNUAL PROGRESS REPORT AND END OF STUDY REPORT	33
11.6.1.	Submission of Documents at Study Start.....	33
11.6.2.	Annual Progress Report.....	33
11.6.3.	End of Study Report	33
12.	AMENDMENTS TO THE CLINICAL INVESTIGATION PLAN	33
13.	EARLY TERMINATION OR SUSPENSION OF THE INVESTIGATION	34
14.	RECORD RETENTION.....	34
15.	STUDY FINANCIAL ARRANGEMENTS.....	35
16.	PUBLICATION POLICY	35
17.	LIST OF ABBREVIATIONS	35
18.	REFERENCES.....	36

List of Appendices

APPENDIX 1	PATIENT INFORMATION SHEET AND INFORMED CONSENT FORM
APPENDIX 2	SAMPLE CASE REPORT FORM

STUDY SUMMARY

Title	Polyethylene Wear Study on the Triathlon Total Knee Prosthesis_A Comparison of a Highly-crosslinked and a Crosslinked PE in-vivo
Protocol Number	TriX3_2009
Phase	Post-marketing
Sponsor	Stryker SA, Montreux, Switzerland
Study design	A Prospective Randomized Single Centre RSA Study
Study Duration	12 months enrolment period + up to 5 year follow-up for each case = 6 years total duration.
Study Centre(s)	1
Objectives	
The primary objective is the assessment of the in vivo wear of the two randomized polyethylene inlay types N2Vac and X3 by means of Roentgen Stereophotogrammetry.
 
The secondary objective is the assessment of prosthetic migration results after two years of the Triathlon CS Peri-Apatite coated tibial component by means of Roentgen Stereophotogrammetry.
 
The third objective will be the prediction of the long-term survival of the Triathlon CS Peri-Apatite coated tibial components based on the two-year migration patterns combined with clinical factors and radiographic aspects.
 
Safety data will be collected

Primary endpoint	In-vivo wear of N2Vac inlay vs. X3 inlay
Indication	Primary total knee replacement
Study device / control device	Triathlon CS total knee system
Number of Subjects	100 Patients

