5.6. Supplies/Device Accountability

The study devices must be stored and handled in accordance with the manufacturer's guidelines. The Investigator will also keep accurate records of the devices assigned to each subject.

The investigator will be asked to attach the labels (with the lot device number), where possible, of the implanted devices to the corresponding patient CRF page in order to keep a tracking of the devices.

6. Methods and Evaluations

Subjects will be evaluated preoperatively, prior to discharge and at follow-up intervals of 6 weeks, 3 months, 6 months, 1, 2 and 5 years. Each subject will be followed for five years post-implantation. At the 1-year follow-up a double examination will be made in order to assess the clinical RSA precision. All subject evaluations will be documented by completion of appropriate Case Report Forms (see Appendix 2).

Table 1 – Evaluation schedule (functional and patient assessment)

	Pre-op	Op	< 1wk (prior to discharge)	6wk	3m	6m	1yr	2yr	5 yr
Range (weeks)				±4d	±1wk	±2wks	±4wks	±4wks	±6ks
Demographic Information	✓								
Historical Record	✓								
Clinical Evaluation			✓	✓	✓	✓	✓	✓	✓
Operative Record		✓							
Knee Society Score	✓			✓	✓	✓	✓	✓	✓
SF-36	✓			✓	✓	✓	✓	✓	✓
EQ 5-D	✓			✓	✓	✓	✓	✓	✓
Lower-Extremities Activity	✓			✓	✓	✓	✓	✓	✓
RSA analysis			✓	✓	✓	✓	✓ (double)	✓	✓
Radiographic imaging	✓ AP/		✓ Lat	✓	✓ Lat	✓	✓ Lat	✓ Lat	✓ Lat

	Lat							
Adverse Events (including revision)		Anytime						

Basic demographic and medical history information is to be collected at the most two months prior to surgery. This information includes age and gender. Height, weight, primary diagnosis, concurrent medical condition and prior treatment to the affected joint are also documented at this time.

Prior to surgery (- 2 months)

Demographic information:	Date of birth Height/ weight Gender	
Patient's initial diagnosis		
Operative side		
Historical record	Cigarette Smoker Medical History: Concurrent Medical condition and current treatment according to medication category (ATC Class)	
Am. Knee Society Score AKSS*	Pain intensity Active and passive range of motion (Neutral-zero-method) Stability Anatomic alignment Walking/standing ability Stair climbing ability Use of walking aids	
Patient questionnaires	SF-36 EQ-5D LEAS (Lower Extremities Activity Scale)	
Radiographic assessment	Anterior/posterior Lateral	

Surgical Procedure

Anesthesia	Type ASA	
Systemic prophylactic therapy	Antibiotic	

	Anticoagulant	
Bone cement		

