Surgical approach		
Soft tissue released		
Navigation		
Deviation from site-specific surgical procedure		
Bone removed	Femur Tibia Slope	
Tantalum balls (ø 1.0 mm)	Position in the tibia bone	
Time	Skin to skin Tourniquet	
Implant details	Sizes of components Product labels	
Intra-operative complications		

Assessment at on week postoperative

Clinical evaluation	Concomitant therapy	Pain medication
	Systemic prophylactic therapy	Antibiotic Anticoagulant
	Rehabilitation/mobilization	Site specific procedure Discharged
Radiographic assessment	Anterior/posterior Lateral Radiostereometric analysis	
Early post-op complications		

Follow-up assessment at 6 weeks, 3 months, 6 months, 1 year, 2 years and 5 years

Clinical evaluation	Patient status	
	Concomitant therapy	Pain medication
	AKSS*	
	Patient questionnaires	SF-36 EQ-5D
Radiographic assessment	Anterior/posterior Lateral Radiostereometric analysis	

Complications		
---------------	--	--

Termination

Date of evaluation		
Study completion	Reason for early termination	
Position of study device at last contact to patient		
Problems at last contact		

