6.1.3 Patient success or failure

Each patient from the two groups must meet the following criteria at the two-year (± 2 months) evaluation in order to be considered as “success”:

Patient Success - defined by the following requirements at the two-year follow-up interval:

- A Knee Score of ≥ 80, and
- No component revisions or removals (femoral, bearing, tibial or patella), and
- No pending component revisions or removals (femoral, bearing, tibial or patella) and
- Absence of Osteolysis in any component (femoral, bearing, tibial or patella) and
- No migration / subsidence of >3mm or >3° in any component (femoral, bearing, tibial or patella)

A patient who meets any of the following criteria at the two-year (\pm 2 months) evaluation will be considered as “failure”:

Patient Failure – defined by the following requirements at the two-year follow-up interval:

- A Knee Score of < 80 , or
- Revisions or removals of any component (femoral, bearing, tibial or patella), or
- Pending revisions or removals of any component (femoral, bearing, tibial or patella), or
- Presence of Osteolysis in any component (femoral, bearing, tibial or patella), or
- Migration / subsidence of 3 mm or $>3^\circ$ in any component (femoral, bearing, tibial or patella).

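### Section 4.3.1 lets the site withdraw a patient for 2-year failure, which can forfeit an obtainable 5-year wear value because of a post-randomisation outcome

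*Combined protocol and SAP*

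**What the plan says.** Section 4.3.1 opens its list with "Subjects may be withdrawn for the following reasons", and the first reason is "Patient failure – defined by the requirements at the two- year follow-up interval see section 6.1.3". For a subject discontinued by the site before the final evaluation, "the subject is notified that they are no longer in the study and a Study Termination form will be completed". After that the protocol provides only for clinical care as needed and specifies no study RSA. Data up to that point are kept: "the information that has already been collected will be included in the database and in the final analyses". Withdrawn subjects are not replaced.

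Section 6.1.3 defines failure at two years as any one of: Knee Score below 80, revision or removal, pending revision or removal, osteolysis, or migration. The osteolysis criterion reads "Presence of Osteolysis in any component (femoral, bearing, tibial or patella), or".

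Section 6 states "Each subject will be followed for five years post-implantation", and its schedule and section 6.3 both include RSA at five years. The Study Summary is looser: "up to 5 year follow-up for each case". Section 2 expects less wear with X3 after five years. Section 9.2 excludes imputation, and section 9.1 plans t-tests with a non-parametric fallback.

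**The concern.** Patient failure is a trial outcome observed after randomisation. Section 6.3 measures wear as the position of the femoral component relative to the tibial component. That needs the components to be in place; it does not need clinical success. A patient with a Knee Score of 75 and the original implant can still give a valid 5-year wear measurement.

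If such patients are withdrawn at two years, the 5-year comparison is restricted to knees that did not fail. Failure may differ by arm and may be related to wear: section 8.2 links osteolysis to polyethylene particles, and section 2 expects less migration with the more wear-resistant insert. At stake is an accurate estimate of the 5-year wear difference, and a 5-year value that was never taken cannot be recovered later. Revision and investigator-judged harm are separate entries in the same list, so the failure entry is not needed for either.

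**Working it through.** **1. The plan's own figure.** Inputs from section 3.2: difference 0.1 mm, SD 0.1, two-sided alpha 0.05, two-sample t-test. The noncentrality is 0.1 / (0.1 × √(2/n)) = √(n/2).

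- n = 27: √13.5 = 3.674, power 95.0%. This reproduces the plan.
- n = 26: power 94.2%, so 27 is the smallest sufficient size.
- n = 50: √25 = 5, power 99.9%.

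Falling from 50 to 27 per group would be a loss of 23/50 = 46%, so lost numbers alone are not the issue.

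**2. Which failures leave wear measurable.** Knee Score, osteolysis and migration failures can occur with all components in place. Pending revision qualifies only if the components are still there at five years. Revision or removal may not qualify.

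**3. Illustration of the size.** The documents give no failure rate, no correlation between failure and wear, and no frequency of use. All three are assumed here.

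- Wear is normal with SD 0.1 and means 0.13 mm/year (N2Vac; the rate in section 3.2) and 0.13 − 0.10 = 0.03 mm/year (X3). The 0.1 mm difference is read as per year.
- Failure occurs when a standard normal liability, correlated ρ with wear within each arm, exceeds a cut-off c common to both arms.
- c is set to give overall failure of 10%, 20% or 30%.
- A fraction u of failures is withdrawn, and only knees with 5-year RSA are compared.

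With wear centred midway between the arms, the cut-offs in liability units are k = c − ρ/2 (N2Vac) and k = c + ρ/2 (X3). The failure rate is p = 1 − Φ(k). Mean wear among the retained knees falls by s = 0.1 × ρ × u × φ(k) / (1 − u × p). The observed difference is 0.100 − s(N2Vac) + s(X3).

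Example with ρ = 0.3, 30% failure, u = 1:

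- c = 0.530, k = 0.380 and 0.680, p = 35.2% and 24.8%.
- s = 0.01718 and 0.01263.
- Difference = 0.100 − 0.01718 + 0.01263 = 0.09545.

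| ρ | All withdrawn (10 / 20 / 30% failure) | Half withdrawn, lowest value |
|---|---|---|
| 0 | 0.100 / 0.100 / 0.100 | 0.100 |
| 0.1 | 0.0997 / 0.0996 / 0.0995 | 0.0998 |
| 0.3 | 0.0974 / 0.0963 / 0.0955 | 0.0986 |
| 0.5 | 0.093 / 0.090 / 0.087 | 0.096 |
| 0.7 | 0.087 / 0.080 / 0.076 | 0.093 |

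**4. Power.** For the example, the retained numbers are 50 × (1 − 0.352) = 32.4 and 50 × (1 − 0.248) = 37.6. With difference 0.0955 and SD 0.1, power is 97.5%. In the most extreme cell (ρ = 0.7, 30%, all withdrawn), power is 94.4% using the smaller SD of the retained knees.

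**5. Sensitivity.** The normal model makes Φ(−0.3) = 38% of X3 knees negative. A non-negative (gamma) model with SDs 0.08 and 0.03 gives the same direction and, over the full range with all withdrawn, 0.099 to 0.069. The 0.076 is therefore not a bound. If half of failures are unrelated to wear, ρ from 0.3 to 0.7 gives 0.098 to 0.082 with all withdrawn. A random-slope analysis that uses RSA up to two years gives 0.096 to 0.100.

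**The case against.** The list may be no more than a set of form entries. It also contains completion of the study, loss to follow-up and death; it follows the sentence on the Study Termination form; and the termination table in section 6 has a field for "Reason for early termination". Nobody is withdrawn for completing. This stands in part: the plan does not say which reading applies, and a reader should not infer that every failure must leave. But the lead-in does permit withdrawal, and the ambiguity is itself a reason to reconcile the wording.

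The link between 2-year failure and wear may be weak. Section 1.1 names wear as a cause of failure after more than two years. Section 8.2 attributes early loosening to fixation, infection, loading or trauma, and places osteolysis under late loosening. Expected wear by two years is 2 × 0.13 = 0.26 mm, against a migration limit of 3 mm. No passage ties the Knee Score to wear. This stands, and it makes the lower correlations the more credible ones.

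The absence of imputation does not establish a completers-only analysis, because data collected before withdrawal enter the final analyses. That is correct, and the figures above depend on this assumption. Section 9.1, however, names no longitudinal method that would use the earlier visits, and retained data do not supply a 5-year value.

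A reader might extend the point to the two serious-adverse-event entries in the same list. No passage links those events to wear, so no bias is shown for them.

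**Conclusion.** The point holds as a narrow one. Section 4.3.1 allows follow-up to end for 2-year failure, which conflicts with the five-year commitment in section 6 (softened by the Study Summary wording) and with the 5-year wear hypothesis in section 2. Where the option is used for a patient with the original components in place, an obtainable wear value is lost because of a trial outcome.

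The size is unknown and probably small. At correlations of 0.1-0.3 and 10-30% failure, the difference shrinks by 0.3-4.5% if every failure is withdrawn, and by at most about 1.5% if half are. With no correlation there is no bias.

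A reader might infer a serious distortion, a false claim for X3 or an underpowered trial. The documents support none of these. Values near 0.076 need a correlation of 0.7, 30% failure (42% against 18% by arm) and every failure withdrawn under an optional rule. If more wear makes failure more likely, as the plan's reasoning implies, the shift is toward zero. Power stays high. This is a cheap improvement of minor to moderate importance.

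**What to change.** Reconcile sections 4.3.1 and 6, and align the Study Summary duration. State that 2-year Patient failure is recorded as an outcome and does not by itself end study follow-up. Keep the scheduled 5-year RSA and clinical visit for patients whose original femoral component, tibial component and randomised insert are all in place, unless consent is withdrawn or the existing investigator well-being criterion applies. State that the 5-year wear comparison includes these knees.

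The same wording may be applied to the two serious-adverse-event entries for consistency. A repeated-measures analysis using RSA up to withdrawal is an optional sensitivity analysis; the planned primary test need not change.

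The cost is a few sentences and at most one visit per failure, already in the schedule. Under the assumed rates that is 10-30 visits among 100 patients if all failures would have been withdrawn, and fewer otherwise. Clinical care is unaffected.

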1.3. Beads

To evaluate the motion of the polyethylene bearing and micromotion of the prosthesis, at least three well-scattered tantalum balls (∅ 1.0 mm) have to be inserted into the tibia and femoral bone. To this end a special designed Ta-marker insertion device will be used according to instructions of the manufacturer (Halifax Biomedical, NS, Canada). The beads are not part of the Knee system itself. The bead inserter

device will be loaned to the hospital by Stryker for the duration of the clinical study (covered in study contract).

2. Objectives of the Clinical Investigation

- The primary objective is the assessment of the in vivo wear of the two randomized polyethylene inlay types N2Vac and X3 by means of Roentgen Stereophotogrammetry. It is expected that the X3 group will show significantly less wear after 5 years compared to the conventional N2Vac polyethylene group.
- The secondary objective is the assessment of prosthetic migration results after two years of the Triathlon CS Peri-Apatite coated tibial and femoral components by means of Roentgen Stereophotogrammetry. It is expected that due to the superior wear qualities of X3 polyethylene this group will show significantly less migration of the prosthesis' components after two-years compared to the components in the N2Vac group.
- The third objective will be the prediction of the long-term survival of the Triathlon CS Peri-Apatite coated tibial and femoral components based on the two-year migration patterns combined with clinical factors and radiographic aspects. In order to identify other clinical parameters besides wear influencing the fixation of the prosthesis components, clinical scores and radiographic aspects will be correlated with the RSA outcome. Subsequently, a long-term prediction can be for the Triathlon CS Peri-Apatite coated tibial and femoral components.

3. Design of the Clinical Investigation

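### An unanswered contact round at any visit leads to study termination with no stated route back, so obtainable 5-year RSA wear values may be forgone

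*Combined protocol and SAP*

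**What the plan says.** Section 4.3.1 sets the rule for patients who do not return for follow-up appointments. Every effort is to be made to reach them. The condition is worded "If after attempting to contact the patient through 3 documented phone calls and a certified (i.e., return-receipt) letter". Where this brings no answer, the rule is mandatory ("the patient still does not respond, the patient will be considered as"), and the status it assigns is loss to follow-up. The consequence follows at once: "A Study Termination Form will be completed after notifying Stryker of the patient's status". The list of reasons earlier in that section is permissive ("Subjects may be withdrawn for the following reasons") and includes loss to follow-up, but the two operative sentences are mandatory. No visit, waiting period or later contact attempt is specified, and nothing is said about a patient who reappears. For a patient who withdraws, the same section keeps earlier data: "the information that has already been collected will be included in the database and in the final analyses". Withdrawn patients keep their subject number and are not replaced.

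Section 9.3 lists a visit outside the specified window among the protocol deviations, and says that for its listed examples exclusion and a Study Termination form are likely. In Table 1 the 6-week window is ±4 days.

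On the other side, section 6 states "Each subject will be followed for five years post-implantation", and section 2 places the primary comparison at the end of follow-up: "It is expected that the X3 group will show significantly less wear after 5 years". Section 6.3 takes the discharge RSA as baseline. Section 9.1 names t-tests or Wilcoxon/Mann-Whitney tests for continuous outcomes. Section 9.2 rules out imputation.

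**The concern.** The plan does not separate a missed visit from the end of study participation. A patient with a good discharge RSA who cannot be reached around an early visit is to be classed as lost and have a termination form completed. A site following the text then has no instruction to invite that patient to the 5-year RSA. Not answering is not withdrawal of consent, and such a patient could still supply the one later measurement that the primary comparison needs.

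Two things are at stake. The first is completeness of the 5-year wear data; for patients terminated before the 2-year visit, the 2-year migration value used for the second and third objectives is also at stake. The second is selection: people who do not respond may differ in activity, health or satisfaction, and so in loading and wear. Recruiting more patients does not correct that.

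**Working it through.** **1. What a primary value needs.** Section 6.3 defines wear as the proximal–distal change of the femoral relative to the tibial component, with the discharge RSA as baseline. A 5-year value therefore needs the discharge and 5-year images. Interim images are not required for it. Section 9.1 specifies no longitudinal model and section 9.2 no imputation. With the two-group tests named, a patient without a 5-year image adds nothing to the 5-year comparison, even though that patient's earlier images stay in the database and the final analyses.

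**2. The plan's own sample size (section 3.2).** Inputs: difference 0.1 mm, SD 0.1 mm in each group, two-sided alpha 0.05, two-sample t-test.

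- Noncentrality = 0.1 / (0.1 × √(2/27)) = √13.5 = 3.67, with 27 + 27 − 2 = 52 degrees of freedom.
- Exact noncentral-t power: 95.0% at n = 27 and 94.2% at n = 26. The stated 27 per group for 95% power is reproduced.

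**3. How much loss the stated power can bear.** The plan recruits 50 per group, partly for loss to follow-up, and gives no loss rate. Tolerable loss = 1 − 27/50 = 46%. Under assumed loss before year 5:

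| Loss | n per group | Power |
|---|---|---|
| 0% | 50 | 99.9% |
| 10% | 45 | 99.7% |
| 20% | 40 | 99.3% |
| 30% | 35 | 98.5% |
| 40% | 30 | 96.8% |
| 46% | 27 | 95.0% |
| 50% | 25 | 93.4% |

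**4. How many 5-year values the rule might cost.** Five post-discharge visits come before year 5: 6 weeks, 3 months, 6 months, 1 year and 2 years. Let p be the chance, at each visit, that a patient misses it and the contact round fails. The documents give no p, so both values are assumptions.

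- p = 2%: 1 − 0.98^5 = 9.6%, or 4.8 of 50 per arm.
- p = 4%: 1 − 0.96^5 = 18.5%, or 9.2 of 50 per arm.
- If half of these could be reached later (also an assumption): 2.4 to 4.6 values recovered per arm. With none reachable the gain is 0; with all reachable it is 4.8 to 9.2.

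**5. What selective loss could do.** If a fraction f of an arm is lost, the completers' mean differs from the full-arm mean by f times the difference between retained and lost patients. As an illustration only, suppose lost patients differ by one planning SD (0.1 mm) in one arm and not at all in the other. The contrast moves by 0.096 × 0.1 = 0.010 mm to 0.185 × 0.1 = 0.018 mm, against a target difference of 0.1 mm. If the pattern is the same in both arms, the shifts cancel in the contrast and only the arm means are affected.

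**The case against.** The strongest case for the plan is that this is a reasonable contact threshold. The text speaks of appointments in the plural, asks for every effort, and requires four documented attempts to fail. Some silence is informal refusal, and repeated letters are a burden on people entitled to leave without giving a reason. Collected data are kept, recruitment carries a large allowance, the rule is the same in both arms, and patients and assessing physiotherapists are blinded, so no mechanism for loss that differs by inlay is evident.

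Most of this stands, and it rules out several stronger readings:

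- A reader might infer that lost status is permanent. The text does not say so; it is silent on re-entry, and a retained subject number would let a returning patient be linked to earlier data. That silence is still a gap, because the operative sentences are mandatory, the form is an end-of-study record, and no later contact is instructed.
- A reader might infer that these patients are dropped from the analysis. Section 4.3.1 keeps what has been collected. What is forgone is the future 5-year measurement.
- A reader might infer a loss of power. On the plan's inputs there is none of consequence.
- A reader might infer that every such label also costs the 2-year migration value. A patient first lost at the 2-year visit has already missed it.
- A reader might see a contradiction with section 6. Its five-year statement gives the planned schedule, and section 4.3.1 handles exceptions.

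What the objection does not answer is that a patient silent at one early visit may be reachable years later, when the value that matters is due, and that the plan directs the site to close the file instead.

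**Conclusion.** The point holds as one of avoidable, possibly selective, loss of 5-year wear values. It rests on three features of the text: mandatory classification and termination after one failed contact round at any visit, no stated route back, and a primary comparison that needs only the baseline and 5-year images with nothing imputed. Section 9.3 adds to it by making exit likely after an out-of-window visit.

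The size is unknown. The 5 to 9 patients per arm depend on assumed rates of 2% and 4% per visit, and the 2 to 5 recovered on the further assumption that half could be reached. The direction and amount of any bias cannot be judged from the documents; the shift of 0.010 to 0.018 mm is an illustration. The power figures assume that the stated 0.1 mm difference and SD apply to the wear measure analysed. Because the remedy is cheap, the plan should be changed, but the matter does not threaten the trial's ability to detect its target difference.

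**What to change.** In section 4.3.1:

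- Record an unanswered contact round as 'visit missed, follow-up continuing'.
- Try contact again at later scheduled visits, at least at 2 and 5 years, unless the patient has refused or withdrawn consent.
- State that a patient who reappears rejoins the schedule at the next visit, including the 5-year RSA.
- Assign lost-to-follow-up status and complete the Termination Form only after the 5-year window has closed without contact.

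In section 9.3, make a missed or out-of-window visit a recorded deviation and not a ground for exclusion or termination.

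The cost is a few sentences of protocol text, some extra calls and letters for non-responders, and study files that stay open longer. The exception for refusal keeps repeated contact from becoming pressure on people who want to leave.
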